5.2. Inclusion criteria

In order to be eligible to participate in this study, a subject must meet all of the following criteria:

- Established homozygous or known heterozygous rare bleeding disorder due to deficiency or dysfunction of fibrin, FII, FV, FV & FVIII, FVII, FX, FXI, FXIII, alpha-2-antiplasmin and PAI-1 ;
- Age 1 year and older;

- For patients ≥ 16 years old; written informed consent.
- For patients 12-16 years old; written informed consent from both the patient and their parents/legal guardian(s).
- For patients <12 years old; written informed consent from their parents/legal guardian(s).

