- X	Factor X deficiency (thrombokinas deficiency)	1:500,000-1 million [1, 2, 5]

	,Stuart-Prower factor deficiency)	
- XI	Factor XI deficiency (plasma thromboplastin antecedent deficiency, Rosenthal syndrome, haemophilia C)	1:1 million [1, 2]
- XII	Factor XII deficiency (Hageman factor deficiency; not associated with bleeding tendency)	
- XIII	Factor XIII deficiency (fibrin stabilising factor deficiency)	1:1-2 million [1, 2]
Fibrinolysis disorders		
- α 2-Antiplasmin	α 2-Antiplasmin deficiency (Miyasato disease)	Unknown, 40 cases reported worldwide [6, 7]
- Plasminogen activator inhibitor type 1	Plasminogen activator inhibitor type 1 deficiency	Unknown, few cases reported worldwide [8, 9]

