Treatment and prophylaxis decisions require frequent venepuncture. Non-invasive testing does not exist yet, but would be extremely beneficial to patients and give way to a future perspective of home-based monitoring combined with home-based treatment. Saliva biomarkers that correlate with anticoagulation status have been identified in coumarin users in Radboud university medical center (unpublished data). RBiN will examine whether these biomarkers correlate with the clinical and laboratory phenotype in patients with rare bleeding disorders and if so, whether we can monitor treatment or rely treatment decisions on these biomarkers.

Precise, personalised treatment of the rare bleeding disorders is hampered by the lack of an adequate test that reflects patients' bleeding potential. At present, treatment decisions are based on clinical phenotype, and standard consensus-based approaches which give the most accurate indication available, but still need fine tuning. Because the Nijmegen

Hemostasis Assay (NHA) measures the key enzymes in both coagulation and fibrinolysis, it might give clinicians a more accurate idea of the haemostatic potential of their patients than currently used tests can. Ideally, this would enable tailored prophylaxis and ad hoc treatment change.

The diagnosis of a rare bleeding disorder is based upon a step-wise conventional laboratory approach as described above (1.4 Laboratory). This strategy is time consuming and expensive, due to the high number of laboratory assays that may be needed (sequentially) to establish a diagnosis. In addition, repeat testing is mandatory for many assays because they are highly variable and dependent on preanalytical and analytical factors. On the other hand, the cost of advanced molecular diagnosis such as whole exome sequencing (WES) is falling, and its practice is ever more common and developed. In addition, WES can trace more genetic abnormalities than current genetic analysis using gene panels can, thereby possibly explaining the differences in bleeding tendency in patients with rare bleeding disorders.

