5. STUDY POPULATION

5.1. Population (base)

Based on the prevalence in the general population of 1:500,000 to 1 per 2 million persons [1, 2], and a total population of 17 million, there should be 129 to 145 individuals with a homozygous rare bleeding disorder in the Netherlands. This could be higher taking into account the possible influences of high-risk populations such as Ashkenazi or Iraqi Jews with high FXI deficiency rates. To date, 337 patients with a rare bleeding disorder are known to the eight Dutch centers that treat such patients. Approximately one third of these patients are homozygous; and around two thirds are heterozygous individuals.¹

All known homozygous and heterozygous patients with a rare bleeding disorder will be invited to participate.

Heterozygous prevalence in the Netherlands have not been evaluated, but can be calculated according to the Hardy-Weinberg principle² to be 93,000 to 99,000 persons, or 0.55% to 0.58% of the Dutch population (5.5 to 5.8 per 1,000 persons) for all rare bleeding disorders combined. Though the estimated number of heterozygous persons in the Netherlands is much higher than the number of persons known to one of the eight treating centers (~179 heterozygous patients³), we expect that the individuals with a known heterozygosity represent a subset with a more severe clinical presentation, who are therefore of interest to our research question.

Characteristics of the Dutch source population

The characteristics of the Dutch population (both homozygous and heterozygous) are largely unknown and are a part of this study. Numbers of known patients per rare bleeding disorder are presented in

[Table 3](#)

[Table 3.](#)

¹ A quick inventory in the Radboud university medical center learned that two thirds of patients were heterozygous individuals whereas one third were homozygous individuals. Based on an inventory of 63 medical files performed on July 8, 2016: 65% missing information, 24% heterozygosity, 11% homozygosity

² The Hardy-Weinberg proportion stipulates that for a single locus with two alleles denoted 'A' and 'a' with population frequencies p and q respectively, the expected genotype frequencies are p² for the AA homozygous individuals, q² for the aa homozygous individuals, and 2pq for the heterozygous individuals. The sum of these frequencies must be 1, thus p² + 2pq + q² = 1 and p + q=1.

Table 3 Prevalence of rare bleeding disorders in the Netherlands

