Deficiency	Estimated prevalence homozygosity in general population as described in the literature [1, 2]	Estimated prevalence homozygosity in the Dutch general population	Patients known at present in the Netherlands (homozygous/heterozygous/unknown)
Fibrinogen	1:1 million	17	28
II	1:2 million	9	9
V	1:1 million	17	22
V & VIII	1:1-2 million	9-17	4
VII	1:500,000	34	92
X	1:1 million	17	10
XI	1:1 million	17	88
XIII	1:1-2 million	9-17	16
PAI-1	Unknown	Unknown	39
Alpha-2-antiplasmin	Unknown	Unknown	29
	Total	129-145	337

Abbreviations: CI: confidence interval

\$ Based on a population figure of 17,024,133 (www.cbs.nl/nl-nl/visualisaties/bevolkingsteller)

* Based on a quick inventory of participating sites, which are all sites in the Netherlands licensed to treat rare bleeding disorders. Homozygosity or heterozygosity largely unknown

Willingness of patients to participate

We expect that a high proportion of patients with rare bleeding disorders are willing to participate in RBiN. Patients are aware of the rarity of their disorder and the lack of research. The Netherlands Hemophilia Society (Nederlandse Vereniging van Hemofilie Patiënten, NVHP) is a co-initiator of RBiN and a patient representative takes seat in the steering committee. Based on the response rate of the HiN studies we expect a (similar) response rate of 70% [51].

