5.3. Exclusion criteria

A potential subject who meets any of the following criteria will be excluded from participation in this study:

- No informed consent given;
- Residency outside of the Netherlands

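### Entry and analysis rest on each centre's existing diagnostic label, and the analysis plan never uses the study's own assays or sequencing to check it

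*Combined protocol and SAP*

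**What the plan says.** Section 5.2 requires established homozygosity or known heterozygosity for a "rare bleeding disorder due to deficiency or dysfunction of fibrin, FII, FV, FV & FVIII, FVII, FX, FXI, FXIII", alpha-2-antiplasmin or PAI-1, together with age and consent conditions. Section 5.3 excludes only for lack of consent and for "Residency outside of the Netherlands". Neither section gives a factor limit, an assay, a second low value or a genotype requirement. Section 5.1 states: "All known homozygous and heterozygous patients with a rare bleeding disorder will be invited to participate".

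The criterion is worded in terms of zygosity. However, the Table 3 footnote says "Homozygosity or heterozygosity largely unknown", a footnote to Section 5.1 reports it missing in 65% of 63 files, and Section 1.4 says genetic testing is not done routinely. In practice the criterion is therefore the centre's label.

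Table 4 takes baseline activity from the records and measures fibrinogen, FII, FV, FVII, FVIII, FX, FXI, FXIII, PAI-1 and alpha-2-antiplasmin afresh. Section 6.2 drops none of these assays in young children and adds exome sequencing in older participants. Section 7 defines no confirmed-diagnosis set, no sensitivity analysis and no rule for a labelled patient whose study results are normal. In Section 2, the account of the usual diagnostic route says "repeat testing is mandatory for many assays because they are highly variable and dependent on preanalytical and analytical factors".

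**The concern.** Three primary outputs take the label at face value: the description of each disorder, the prevalence with its 95% confidence interval, and the regression linking factor activity to clinical bleeding severity. A patient who bleeds for another reason and carries a label that the study's own data do not support would add to the first two. In the third, that patient would appear as someone who bleeds at a near-normal level. Enough such patients would weaken the level-severity relation and distort the check of the published levels for staying free of symptoms.

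This matters here because a weak link between level and bleeding is part of the study's rationale (Summary and Section 2). An artefact in that direction would look like confirmation. The protocol itself names routes to a low value that are not inherited disease: assay variability (Section 2), acquired disease and anticoagulant use (Section 1.4), and the fall of alpha-2-antiplasmin with age (Section 1.2). None of these reaches the eligibility criteria or the analysis.

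**Working it through.** **1. The plan's own count.** Table 3, known patients: 28 + 9 + 22 + 4 + 92 + 10 + 88 + 16 + 39 + 29 = 337, which reproduces the stated total.

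**2. The two fibrinolysis disorders.** 39 + 29 = 68, and 68/337 = 20.2%. At the 70% response expected in Section 5.1, 0.7 × 68 = 47.6 of 0.7 × 337 = 235.9, or about 48 of 236 participants.

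**3. Table 1 against Table 3.** For alpha-2-antiplasmin, 29 Dutch patients stand against 40 cases reported worldwide (29/40 = 72.5%). If one third are homozygous, the share assumed in Section 5.1 for all disorders, this is about 10 of 40 (24%). For PAI-1, 39 stand against only a few reported worldwide. Table 1 is headed as homozygous prevalence, whereas the Table 3 column mixes homozygous, heterozygous and unknown. The comparison is therefore not like with like.

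**4. What is at stake if some labels fail.** The documents give no rate. If 25%, 50% or 100% of the 68 were unconfirmed, that would be 17, 34 or 68 people, or 5%, 10% or 20% of 337. These are illustrations and not estimates.

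**5. What one further value can do.** Assume a label resting on a single value below a limit set at the 2.5th or 5th percentile, in a person without disease, with bivariate normal repeat values. The chance that the second value is also low is P(both low)/P(first low):

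| Test-retest correlation | 0 | 0.5 | 0.7 | 0.8 | 0.9 |
|---|---|---|---|---|---|
| 2.5th percentile | 0.025 | 0.19 | 0.33 | 0.44 | 0.59 |
| 5th percentile | 0.05 | 0.24 | 0.39 | 0.50 | 0.64 |

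A second value would thus remove between 1 − 0.64 = 36% and 1 − 0.025 = 98% of pure chance-low labels. It is a useful check but not a complete one.

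**6. What restricting to confirmed patients does to the Section 7.1 regression.** There, factor activity is the dependent variable. Suppose all patients are genuine, confirmation is by laboratory value only, and level and severity are bivariate normal with correlation ρ. If the top share d of levels is dropped, the slope is multiplied by θ/[1 − ρ²(1 − θ)]. Here θ is the variance of the remaining levels relative to the full variance: θ = 1 − c·m − m², with c the (1 − d) normal quantile and m = φ(c)/(1 − d).

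- d = 10%: c = 1.2816, m = 0.195, θ = 0.712. The factor is 0.731 at ρ = 0.3 and 0.767 at ρ = 0.5, so the slope shrinks by 27% and 23%.
- d = 30%: c = 0.5244, m = 0.497, θ = 0.493. The factor is 0.516 at ρ = 0.3 and 0.564 at ρ = 0.5, so the slope shrinks by 48% and 44%.

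With severity as the outcome and level as the predictor, the same restriction leaves a linear slope unchanged in expectation, because selection is then on the predictor.

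**The case against.** The case for leaving entry as it is has weight. The Table 3 count is "Based on a quick inventory of participating sites, which are all sites in the Netherlands licensed to treat rare bleeding disorders", so the labels come from specialist centres. The Section 2 sentence on repeat testing describes how these diagnoses are normally reached, which suggests that many labels already rest on more than one value. A broad population is a legitimate choice for a descriptive study of all known patients. Section 5.1 also says that known carriers are of interest. All of this stands, and it is why all participants should remain the main set.

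Three stronger readings are tempting, and the documents support none of them.

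- *Chance low values are being counted as disease.* Nothing in the documents shows this. They show only that it can happen and that the plan would not detect it.
- *The PAI-1 and alpha-2-antiplasmin counts prove false labels.* In-scope carriers could explain them. Known patients also exceed expected homozygotes for FVII (92 against 34) and FXI (88 against 17), and Section 1.1 says registries and case series tend to undercount.
- *The chance that a healthy person has at least one low value among nine assays measures mislabelling.* That calculation assumes independent assays, all nine run in everyone. Sections 1.4 and 2 describe stepwise testing of people suspected of bleeding. It says nothing about the 337.

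One could also say that normal study values will be visible in the descriptive tables. That is only partly true: no count of them is planned, and the prevalence and regressions would still include those patients without distinction.

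The objection to making a confirmed set primary stands in full. It would select on the dependent variable and take out mild carriers.

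**Conclusion.** The gap is real and cheap to close. Eligibility and analysis depend on the label, and results that could check it are collected but not used for that purpose. Its effect on the counts, the prevalence and the level-severity slope cannot be sized from the documents, because they give neither reference limits, nor assay reliability, nor the number of labels backed by repeat values or genotype. The 68 patients (20% of 337) mark where the warning is most visible and are not an estimate of error. The illustrations in the working rest on assumed normality, limits, correlations and shares dropped. The point supports a pre-specified flag and a sensitivity analysis. It does not support narrower entry or a confirmed-only primary analysis.

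**What to change.** Keep entry and the main analysis set as they are. Before analysis, define a confirmed flag for each disorder. A participant is confirmed if either holds:

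- activity is below the measuring laboratory's lower limit on both the recorded baseline and the study sample (baseline only for patients on replacement); or
- there is a pathogenic variant in the disorder's gene.

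Then:

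1. Report counts and prevalence for all, confirmed and unconfirmed patients. The flag exists only for participants, so state the denominator. Show separately those unconfirmed because a value is missing.
2. Repeat the primary description and regressions in the confirmed set as a pre-specified sensitivity analysis.
3. State that restricting on factor activity truncates the dependent variable of the Section 7.1 regression, so that a flatter confirmed-set slope is read with this in mind. Alternatively, make severity the outcome and level the predictor in that analysis.
4. Settle two details that the flag needs. Table 4 does not say whether PAI-1 and fibrinogen are measured as activity or antigen. Section 6.2 rules out sequencing under 16 in one place and plans it for everyone over 12 in another.

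The cost is an analysis-plan definition built mainly on data already planned, with no added blood. The downside is that some true mild carriers, and some children without sequencing, will fall in the unconfirmed group. Section 1.5 also notes that conventional genetic testing finds no mutation in roughly 10% to 20% of patients. Unconfirmed should therefore be reported as not confirmed by these data, and not as free of the disorder.

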5.3. Exclusion criteria

A potential subject who meets any of the following criteria will be excluded from participation in this study:

- No informed consent given;
- Residency outside of the Netherlands

6. METHODS

6.1. Study procedures

Patients will be approached by their own treating physician. Data will be collected through questionnaires, a clinical interview, a blood and saliva sample obtained from each participant, and thorough review of electronic patient records. An overview of study procedures is given in Table 4. All procedures are study related. In case a physician visit with the treating physician is already planned, or in case a venepuncture for regular diagnostics or treatment is already planned, this can be combined with the study procedures to prevent an extra visit.

Table 4 Overview of study procedures for each adult subject

Procedure	Outcome
Study physician visit	

 Clinical interview 	
 Bleeding score (ISTH-BAT) RBD bleeding score[52] Children: iCHEC
Questionnaires	

 Self-administered 	
 Demographic characteristics (generic) Socio-economic characteristics (generic) Clinical characteristics (bleeds, treatment), HIV status (patients born before 1985) and hepatitis C status (patients born before 1992) Medical history (generic) Sexuality (generic) General health status (Rand-36/Cho-KLAT) Sports and physical activity (MAQ/HeptestQ) Adherence (VERITAS-pro) Pain (generic) Needle phobia (generic) Experience with care (generic)
Electronic patient records	
	
 Date of birth Sex Baseline factor activity level Baseline factor antigen level Treatment type (prophylactic treatment or on-demand treatment) Body weight and height Bleeding score at diagnosis Relevant previous medical history, i.e. arterial thrombosis, atherosclerosis, medication use, pregnancies and outcomes
Blood samples: 72-83 ml	

 Haemostasis 	
 Screening tests - PFA - Haemoglobin

		
 - Thrombocytes - VWF ristocetin cofactor - VWF antigen - VWF collagen binding assay - FVIII act one stage - FVIII chromogen - aPTT - PT - Fibrinogen - Thrombin time 	
 - Leucocytes & differentiation - Peripheral blood smear - Creatinine - ALAT - TSH - D-dimer - Antitrombin - Protein C - Protein S - TFPI
	
 • Diagnostic tests 	
 - FII - FV - FVII - FIX 	
 - FX - FXI - FXII - FXIII
	
 • Global assay 	
 - Nijmegen Haemostasis Assay 	

 • Fibrinolysis 	
 • PAI-1 • TPA • Plasminogen 		
 • α2 –antiplasmin • TAFI

 • Other 	
 • DNA (whole exome sequencing) • Inhibitor assays (only in people ever treated with clotting factors) • Lupus anticoagulans • Anti β2 glycoprotein I 		

 • Biobank 	
 • 2 x 10 ml citrate 		
Saliva sample			

 • Coagulation 	
 • Biomarkers of coagulation 		

Abbreviations: ISTH-BAT: International Society on Thrombosis and Haemostasis/Scientific and Standardization Committee Bleeding Assessment Tool

6.2. Data collection

Questionnaires

Patients will receive a personal log on code to an electronic questionnaire after informed consent. They will be reminded after one month to fill out the questionnaire online. Patients unwilling or unable to fill out the questionnaire electronically will be provided with a hard copy of the questionnaire. The questionnaires can be found in separate documents. Children’s versions of the questionnaire will be available for children up to 17 years old. Whenever possible, questionnaires specifically validated and designed to be filled out by children will be used. In general, children from 12-17 years old will be able to fill out the questionnaire independently. For children under 12 years old, parents will fill out most of the questions.

The complete questionnaire will take approximately 40-120 minutes to complete, depending on which questions are relevant to the patient. For example, the haemophilia activity list of approximately 50 questions will only be filled out by patients with chronic joint impairment, a

minority in this patient group. The VERITAS-PRO questionnaire will only be performed in patients who are on prophylaxis and patients born after 1992 will not fill out questions about hepatitis C and HIV infections. There are also parts of the questionnaire only for women or certain age-groups. Therefore, we expect that close to no patients will have to fill out all the questions. The questionnaire can be paused at any time and continued later on.

The patients will submit the questionnaires digitally. The questionnaires will be checked and discussed briefly to verify during the patient visit. [The bleeding scores are entered directly into the eCRF.](#)

Blood sampling

All participants will be asked to provide a blood sample during a visit to the haemophilia treatment center. Sampling of 1-5% of an individual's total blood volume is deemed safe according to a systematic review of the literature and of existing guidelines[53]. For this study we will set the maximum around 2.5% of the total blood volume, or 2mL/kg based on a total circulating blood volume of 80mL/kg in persons weighing 2kg or more.

In adults and children ≥ 12 years old, roughly 67 ml blood will be drawn through a study-related venepuncture. Forty-seven ml of this sample will be used for this study while the remaining 20 ml will be stored in the Radboud university medical center Biobank for future research. Additional information about the Biobank is provided in separate documents.

Blood samples will be used for the experiments specified in table 4.

In children under 16 years of age, whole exome sequencing will not be performed. Also, the following tests are not performed under 12 years of age: ALAT, TSH, creatinine, lupus anticoagulans and d-dimer. Therefore, only 47mL of blood will be needed for these children. For children under 8 years of age, in addition there will be no blood drawn for the biobank so that they only need to supply 27mL of blood.

Remaining material can be used for future research. In this case, studies will be performed according to the protocol Biobank Hematologie HEMBB (IRB Registration number: CMO Arnhem-Nijmegen 2013/064). In case the research would not be within the scope of HEMBB, the CMO will be consulted in advance.

Saliva sampling

Whole saliva will be collected in the morning when patients did not drink more than 2 glasses of alcohol on the evening before and did not eat 1 hour before collection. In case of infections

in the oral cavity or a severe cold, patients will be excluded. Before saliva collection the mouth will be rinsed with water and donors will be allowed to chew on 25 cm² sheet of parafilm (Parafilm® M) for 1 minute. Produced saliva will be collected into a 50 ml tube and centrifuged at 10,000g for 10 minutes. Samples will be divided in aliquots of 250 µl and stored at -80°C. Stimulated whole saliva collection will be used because of its non-invasive approach instead of e.g. glandular saliva donation, and since stimulated whole saliva has been found to have a large portion of peptides and proteins derived from the parotid glands. Specimens will be processed with several techniques including ELISA and proteomics.

Saliva samples are only collected in patients ≥4 years old.

Electronic patient records

The clinical data will be collected from the medical charts by the research team using a case report form. Each patient will be assigned a unique study code, as described XXXX. A copy of the case report form will be sent to the coordinating center (Radboud university medical center) for data entry and a copy will be kept at the original center.

Whole exome sequencing

In all patients over 12 years of age, whole exome sequencing will be performed. A filter will be used to get the results of 135 bleeding related OMIM-proved genes involved in haemostasis.

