8.4. Benefits and risks assessment, group relatedness

There is a possible minor bleeding risk for people participating in this study connected to collection of blood. However, this is a very minor risk considering the experience of patients and nurses. Blood of patients having RBDs is routinely tested during regular visits to treatment centers and risks associated to blood sampling are considered to be negligible.

Patients will not directly benefit from participating in this study but in the long term this study contributes to our knowledge of the rare bleeding disorders and will increase awareness of these disorders amongst health care workers, as such improving diagnostics and care.

Since the population of patients having RBDs is very small, it is important to include all patients, also minors (children <18 years), in the study (around one third of known patients are minors). Therefore this study may be regarded as group-related.

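### The 27 mL draw for children under 8 is set by age alone and exceeds the study's own maximum of around 2 mL/kg in any child under 13.5 kg, while enrolment starts at age 1

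*Combined protocol and SAP*

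**What the plan says.** Section 6.2 (Blood sampling) begins with a safety range taken from a cited review: "Sampling of 1-5% of an individual's total blood volume is deemed safe". It then adopts a tighter limit of its own: "we will set the maximum around 2.5% of the total blood volume, or 2mL/kg based on a total circulating blood volume of 80mL/kg".

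The same subsection sets the volumes by age band:

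- from age 12: roughly 67 mL, of which 20 mL is for the biobank;
- under 12: 47 mL, after several tests are omitted;
- under 8: no biobank sample either, "so that they only need to supply 27mL of blood".

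Blood is asked of all participants, and the age criterion in section 5.2 is "Age 1 year and older". Saliva has a lower age limit of 4 years. Blood has no lower limit by age or weight beyond eligibility itself. Table 4 in section 6.1 lists "Body weight and height" among the items taken from patient records, but the plan does not link body weight to the volume drawn.

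**The concern.** A per-kilogram limit and a volume fixed by age can both be met only above a certain weight. The lowest band gives a 1-year-old and a 7-year-old the same 27 mL, so the lightest eligible children are the ones in whom the two rules are likely to collide.

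Two things are at stake. A centre that follows the 27 mL figure takes more than the study's stated maximum from its smallest participants, who are minors with a bleeding disorder. A centre that follows the maximum has to leave assays out, and no order is given. With eight treating centres, different choices could make the missing laboratory data differ by centre. The analytical loss is limited, because Table 4 takes "Baseline factor activity level" and the baseline antigen level from records. It would fall mainly on assays that need the study sample, such as the Nijmegen Haemostasis Assay.

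**Working it through.** **Inputs from the protocol.** Cap of around 2.5% of blood volume; blood volume 80 mL/kg; volumes of 67, 47 and 27 mL by age band; biobank sample 20 mL; safe range 1-5% (all section 6.2). Minimum age 1 year (section 5.2). 337 known patients and the expected response (section 5.1). Share of minors (section 8.4).

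**Input assumed.** Body weights, because the documents give none. The range used is 8 to 12 kg for the youngest children.

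**Reproducing the plan's figures.** 0.025 x 80 = 2.0 mL/kg, as stated. The volumes also reconcile: 67 - 20 = 47 mL for the study from age 12, and 47 - 20 = 27 mL under age 8. The sums are right; the conflict is between the cap and the volume.

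**Weight at which the 27 mL draw meets each limit** (volume / limit per kg):

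- study cap: 27 / 2.0 = 13.5 kg;
- cap read loosely as 3%: 0.03 x 80 = 2.4 mL/kg, so 27 / 2.4 = 11.25 kg;
- upper end of the safe range: 0.05 x 80 = 4 mL/kg, so 27 / 4 = 6.75 kg.

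**Size of the excess.** The share of blood volume is 27 / (80 x weight), the volume allowed is 2 x weight, and the excess is 27 minus that.

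| Weight (assumed) | mL/kg | % of blood volume | Allowed by cap | Excess | Excess as % of 27 mL |
|---|---|---|---|---|---|
| 8 kg | 3.38 | 4.2% | 16 mL | 11 mL | 41% |
| 10 kg | 2.70 | 3.4% | 20 mL | 7 mL | 26% |
| 12 kg | 2.25 | 2.8% | 24 mL | 3 mL | 11% |
| 13.5 kg | 2.00 | 2.5% | 27 mL | 0 mL | 0% |

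**How many children, as an illustration.** Section 8.4 says that "around one third of known patients are minors", and section 5.1 says "we expect a (similar) response rate of 70" per cent. Then 337 / 3 x 0.70 = 78.6 minors. If ages are uniform over the 17 years from 1 to 17, and only children aged 1-2 weigh under 13.5 kg, the count is 78.6 x 2/17 = 9.3. If that holds for ages 1-3, it is 78.6 x 3/17 = 13.9. That gives about 9 to 14 children.

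**Other bands.** The cap is met from 47 / 2 = 23.5 kg in the 47 mL band and from 67 / 2 = 33.5 kg in the 67 mL band, so a light child in either band could also be over it.

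**A separate, minor mismatch.** Table 4, headed for adult subjects, gives 72-83 mL where the text gives roughly 67 mL. The difference is 72 - 67 = 5 to 83 - 67 = 16 mL, and both totals include the 20 mL biobank sample.

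**The case against.** The strongest reply is that a maximum, stated just before the volumes, naturally governs them. On that reading, 27 mL is what the reduced panel needs and not a mandated draw. This may well be the intention, but it does not settle the matter. No text says that the draw is scaled down, and if it is, up to 41% of the sample at 8 kg goes without a rule for what to omit.

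Second, the cap is worded as approximate, so the 13.5 kg edge is softer than it looks. This stands in part. A child of 12.5 to 13.5 kg is over by at most 0.16 mL/kg (27 / 12.5 = 2.16), and on a 3% reading a 12 kg child is within the limit. A 10 kg child, at 3.4%, is over on either reading.

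Third, the draw stays within the 1-5% range at every weight considered. That is correct and limits the seriousness.

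Fourth, the effect on results is uncertain. The documents give no volume per assay, the analyses are largely descriptive and exploratory, and differences between centres arise only if centres choose differently. This also stands: the effect on the data is possible, not shown. The count of children is equally soft, because its range varies only the ages assumed to be under 13.5 kg and holds the response rate and age distribution fixed.

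Finally, the Table 4 mismatch is a different issue, and an adult range can be legitimate because inhibitor assays are done only in people ever treated with clotting factors. It carries no weight in the conclusion.

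**Conclusion.** The concern holds. As written, the under-8 volume breaks the study's own maximum in any child below 13.5 kg, and below 11.25 kg even if the cap is stretched to 3%. The threshold rests only on figures in the protocol and is exact. The size of the excess, 3 to 11 mL at 8 to 12 kg, depends on assumed weights. The count of about 9 to 14 children depends on further assumptions about age, response and weight, and is only indicative. No breach of the protocol's 1-5% range is claimed above 6.75 kg. The point should be fixed because it concerns a stated limit for the smallest participants and costs almost nothing to correct.

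**What to change.** State in section 6.2 that the maximum governs: the volume drawn is the smaller of the age-band volume and 2 mL x current body weight in kg. That gives 16 mL at 8 kg, 20 mL at 10 kg, 24 mL at 12 kg and the full 27 mL from 13.5 kg. Apply the same rule to the 47 mL and 67 mL bands, where it binds below 23.5 kg and 33.5 kg. Weight is already a data item, but a current value has to be available at the visit before sampling.

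Add a fixed order in which assays are omitted when the cap binds, so that all centres leave out the same ones, and record the volume drawn.

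As a separate tidy-up, make the adult total in the text agree with Table 4. If a range is intended, say what it depends on.

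The cost is a few sentences of protocol wording and some missing assays in the smallest children, who would give 3 to 11 mL less blood at the assumed weights.
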